6.1.3 Additional Subject Qualification Criteria to Receive Allergy Testing

Subjects classified as low-risk after administration of the PCN (B-lactam) allergy history screening questionnaire and who meet any of the following criteria will be ruled out for skin testing and/or direct oral challenge:

- Known (per medical record or self-report) Human Immunodeficiency Virus (HIV) which is not controlled (defined as any of the following):
 - Not on Highly Active Antiretroviral Therapy (HAART)
 - CD4 <200 in the last 6 months
- Use of oral antihistamines within 1 week of visit. (Subjects can be advised to stop antihistamines and return after 7 days)
- Diffuse eczema, psoriasis, tattoos or other skin condition that would preclude skin testing
- Tachycardia: Pulse >100
- Tachypnea: Respiration rate >16

- Elevated blood pressure (BP) defined as either systolic >160mm or diastolic >100mm
- Uncontrolled asthma or wheezes present on physical exam (PE)
- Angioedema present on PE
- Stridor of throat, tonsils or uvula, or stridor present on PE
- Maculopapular rash or disseminated pruritis on >2 body areas which developed within 1 week prior to the visit.*

Note: This exclusion does not apply to subjects with psoriasis or other chronic skin conditions. These subjects qualify if the forearm where the skin testing is performed is uninvolvled.

6.2 PCN Skin Testing

Depending on the outcome of the PCN (B-lactam) allergy history screening questionnaire, participants may qualify to receive the PCN skin test.

- Participants with a higher risk of PCN allergy will not proceed to the PCN skin test or oral challenge. Their study participation will be complete. Subjects will be provided with a written referral to local allergy providers.
- Participants with a low risk of PCN allergy and assigned to the PST intervention group will be offered the PCN skin test.

Staff will verify that qualified participants do not meet any additional criteria that would preclude them from skin testing using the Skin Test Qualification Checklist. Study staff will explain the skin testing procedures to participants who may decide to accept or decline skin testing. If they decline, they will be asked to complete the subject acceptability survey and their study participation will be complete. Staff will note the reason(s) they declined to be skin tested on the appropriate CRF.

Study staff will perform the allergy skin testing for PCN allergy in accordance with standard allergy testing procedures and instructions provided in the PRE-PEN® kit package insert.³¹ Prick (Puncture) tests will be performed before proceeding to intradermal testing. Prick testing is performed at marked sites on the inner volar aspect of the forearm. Testing for controls and each reagent is performed singly.

Reagents and controls for prick and intradermal tests include:

1. Controls:
 - a.) Negative Control: Sodium chloride solution without preservative

* e.g., patients presenting with secondary syphilis

- b.) Positive Control: Histamine:
 - i. Prick testing: histamine base 1 mg/ml
 - ii. Intradermal testing: histamine base 0.1 mg/ml
2. Reagents:
 - a.) PRE-PEN® (major determinant)
 - b.) Penicillin G 10,000 U/ml (minor determinant)

Intradermal testing will not be performed if there is a positive or uninterpretable reaction to PRE-PEN® and/or Penicillin G during the prick test. If the prick skin test results are negative the participant is qualified for intradermal testing. Study staff will perform duplicate intradermal skin testing of each reagent and single intradermal skin testing of the positive and negative controls on the inner volar aspect of the forearm. The same arm will be used for both prick and intradermal testing.

If there is a positive reaction to PRE-PEN® and/or Penicillin G during the prick test or the intradermal test, the participant is ruled out of the oral challenge with amoxicillin 250 mg. They will be counseled that their PCN allergy history was confirmed. Written documentation will be provided to the subject with instructions to share with their medical provider(s).

If the result of the intradermal test is ambiguous (equivocal), the intradermal test will be repeated with both reagents and the negative control in duplicate or, depending on each study clinic's procedures, the subject will be referred to a local allergy consultant or clinic. If the repeat intradermal test is positive or ambiguous or the initial reaction was uninterpretable, the participant will not proceed to the oral challenge and will be referred to an allergist for further evaluation.

Study staff will photograph the subject's arm to document the results of the skin test reactions using an iPad. No identifiers except a label containing the PN and a measuring guide will be included in the photograph. The images will be uploaded to the clinical database. Complete skin test responses (both prick and intradermal) will be recorded on the PCN skin test results CRF.

Occasionally, allergy skin tests can produce a severe, immediate allergic reaction. These are largely eliminated by doing the preliminary prick skin test. These can be treated with antihistamines, steroids or both. Infrequently, these symptoms this can require immediate medical treatment with epinephrine.

6.2.1 Oral Challenge Following a Negative Skin Test

In PST group subjects with negative skin test results, the absence of allergy will be confirmed by administering a single oral dose of amoxicillin 250 mg followed by one hour of observation to ensure that an immediate reaction does not occur.

6.3 Amoxicillin Oral Challenge

Study staff will explain the oral challenge testing procedures to all qualified participants in both allergy validation intervention groups who may decide to accept or decline the oral challenge. If they decline, they will be asked to complete the subject acceptability survey and their study participation will be complete. Staff will note the reason(s) a subject declined to take the oral challenge on the appropriate CRF.

For those who consent to oral challenge, study team will perform a focused PE and record vital signs (including peak flow) on the oral challenge testing results CRF before the oral challenge is performed. The focused PE will include:

- Eyes: Documentation of no angioedema
- Pharynx: Documentation of no stridor
- Lungs: Documentation of no wheezing or uncontrolled asthma
- Skin: Documentation of no maculopapular rash, disseminated pruritis or urticaria

Staff will verify that qualified participants do not meet any additional criteria that would preclude them from oral challenge using the Oral Challenge Qualification Checklist. At baseline, if subjects have pulse >100, respiration rate >16, or elevated BP (defined as systolic >160mm or diastolic >100mm), the oral challenge will not be performed. Additional reasons assessed during the focused PE for not receiving the oral challenge are listed in Section 6.1.3 and summarized in the listing above.

6.3.1 One-step Oral Challenge (PST Group)

After confirming the participant is qualified, amoxicillin 250 mg will be administered, and time of administration will be recorded. The subjects will be observed for 60 minutes \pm 10 minutes, after which vital signs, the PE and peak flow will be repeated. Note that each observation time point has a time window of +/- 10 minutes.

If subjects report the presence of difficulty breathing, swelling in lip/mouth/tongue/throat, eye itchiness/tearing, skin hives/itchiness or abdominal pain/nausea/vomiting while they are waiting for final evaluation, study staff will include the reactions with the post-oral challenge vital signs and the focused PE assessment performed after the 60-minute observation period \pm 10 minutes. Standard treatment will be provided, including antihistamines, steroids and/or epinephrine, if indicated and dependent on the specific medical condition that arises.

If vital signs (including peak flow) and focused PE are within reasonable limits after the 60-minute \pm 10 minutes waiting period, the subject will be counseled that they do not have an allergy to PCN (B-lactams). They will be provided with written documentation that they will be encouraged to share with their medical providers, including the STD clinic and their primary care physician (if they have one).

6.3.2 Two-step Direct Oral Challenge (DOC Group)

Preliminary Dose

After confirming the participant is qualified, amoxicillin 25 mg will be administered, and time of administration will be recorded. The subjects will be observed for 30 minutes \pm 10 minutes, after which vital signs including peak flow will be repeated.

Administration of Full Challenge Dose

If vital signs are within reasonable limits after the 30-minute \pm 10 minutes waiting period, the subject will be given the full challenge dose of 250 mg amoxicillin. The subject will be observed for an additional 30 minutes \pm 10 minutes, after which vital signs, the PE and peak flow will be repeated.

If subjects report the presence of difficulty breathing, swelling in lip/mouth/tongue/throat, eye itchiness/tearing, skin hives/itchiness or abdominal pain/nausea/vomiting while they are waiting for final evaluation, study staff will include the reactions with the post-oral challenge vital signs and the focused PE assessment performed after 30-minute \pm 10 minutes observation period. Standard treatment will be provided, including antihistamines, steroids and/or epinephrine, if indicated and dependent on the specific medical condition that arises.

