6.1.2.2 Procedures After Defining Risk Category

Subjects classified with a low-risk history will progress to either skin testing (PST Group) or direct oral challenge (DOC Group), depending on which method of validating PCN allergy they are assigned. Subjects who meet the higher-risk classification will be advised that further elucidation of their allergy status will require a formal allergy evaluation. Referral resources will be provided.

All participants classified as low-risk and who meet additional qualification criteria to receive allergy testing (See Sec 6.1.3) will undergo the following procedures:

ASSIGNED TO PST GROUP

- Administration of skin test (prick test first and, if indicated, intradermal test)
- If skin test results are negative, option to receive oral challenge of 250 mg of amoxicillin
- Pre-oral challenge brief PE, assessment of vital signs and measurement of peak flow
- Administration of oral challenge
- Post-oral challenge brief PE, vital sign assessment and peak flow measurement

ASSIGNED TO DOC GROUP

- Pre-oral challenge brief PE, assessment of vital signs and measurement of peak flow
- Administration of oral challenge (first step) of 25 mg of amoxicillin, vital sign assessment and, if indicated, administration of oral challenge (second step) of 250 mg of amoxicillin
- Post-oral challenge brief PE, vital sign assessment and peak flow measurement

All participants will undergo the following procedures after allergy validation methods are offered or completed:

- Administration of subject acceptability survey on PCN testing procedures for all subjects who were offered skin testing (with or without oral challenge) or direct oral challenge
- Written documentation of PCN allergy testing results for all subjects who received skin testing (with or without oral challenge) or direct oral challenge to share with subject's medical care providers

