6.3.3 Final Outcomes and Determination of Allergy Status

If vital signs (including peak flow) and focused PE are within reasonable limits after the applicable observation periods, subjects will be counseled that they do not have an allergy to PCN (B-lactams). They will be provided with written documentation that they will be encouraged to share with their medical providers, including the STD clinic and their primary care physician (if they have one).

Final outcomes of the oral challenge will be recorded on a CRF as no reaction (negative), reaction (positive) or unevaluable (if the participant leaves the clinic before the applicable observation period is completed). If there is a reaction, after providing standard treatment, study staff will record the type of reaction, severity and how long after the amoxicillin was administered it occurred on the oral challenge testing results CRF.

If reactions to the amoxicillin oral challenge occur, they will be graded and documented using the Toxicity Table (Appendix C).

Rarely, an oral challenge in an individual who skin tests negative can produce an acute reaction (e.g., anaphylaxis) requiring emergency care. Unexpected reactions that place a subject at increased risk will be treated as necessary and reported to the IRB and DMID as required.

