APPENDIX C: TOXICITY TABLE

Clinical Adverse Events			
NEUROLOGICAL/ CARDIOVASCULAR	Mild (Grade 1)	Moderate (Grade 2)	Severe (Grade 3)
Pre-syncope/Syncope	Lightheadedness	Dizziness (pre-syncope), diaphoresis and sense of impending doom	Confusion, collapse, loss of consciousness
Hypotension			Decrease in systolic blood pressure greater than 30% from baseline
Pulse		Increase or decrease of 20bpm from baseline	Increase or decrease of 30bpm from baseline
CUTANEOUS	Mild (Grade 1)	Moderate (Grade 2)	Severe (Grade 3)
Urticaria and angioedema	Flushing or sensation of heat or warmth	Generalized urticaria and/or periorbital edema or angioedema (not laryngeal, tongue or uvular)	Generalized urticaria and laryngeal, tongue or uvula swelling with or without stridor
HEENT	Mild (Grade 1)	Moderate (Grade 2)	Severe (Grade 3)
Eyes, face and periorbital area	Conjunctival erythema, pruritus or tearing	Conjunctivitis plus rhinitis (e.g., sneezing, rhinorrhea, nasal pruritus and/or nasal congestion),	
Upper respiratory		Cough perceived to come from the upper airway (not the lungs, larynx, or trachea) without stridor	Upper respiratory symptoms and cough perceived to come from the lungs, larynx, or trachea with stridor
RESPIRATORY	Mild (Grade 1)	Moderate (Grade 2)	Severe (Grade 3)

Shortness of breath (bronchospasm)	Transient; no treatment; 71% - 80% of baseline peak flow	Bronchospasm (dyspnea, hoarseness, wheeze) that requires medical intervention; normalizes with bronchodilator; 60% - 70% (of baseline peak flow)	<60% of baseline peak flow Bronchospasm that does not resolve or progresses to respiratory failure
GASTROINTESTINAL	Mild (Grade 1)	Moderate (Grade 2)	Severe (Grade 3)
Abdominal cramps, vomiting or diarrhea	Transient abdominal cramps	Abdominal cramps, nausea, vomiting or diarrhea	Abdominal cramps, nausea, vomiting or diarrhea with signs/symptoms of dehydration that requires medical intervention

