7. SKIN TESTING GROUP

- a. Verify skin test reagents correctly labeled _____
- b. Skin Prick Targets Marked appropriately _____
- c. Skin Pricks administered in the correctly labeled area _____
- d. Positive and Negative Controls Correct _____
- e. Intradermal Targets Mapped and Marked _____
- f. Intradermal Tests administered _____
- g. Waiting Time Appropriate _____
- h. Positive and Negative Controls Correct _____
- i. If positive, photograph and document _____

8. Oral Challenge (After Skin Testing)

- a. Physical assessment and Vital Signs time =0
(Peak Flow: Use highest value of 3 successive readings) _____
- b. Oral Challenge administered _____
- c. Physical assessment and Vital Signs time =60 min. _____
- d. Results Explained to Subject _____

**Validate an Easy to Administer Algorithm to Define Penicillin (B-lactam) Allergy Status in STD
Outpatients**

DMID Protocol Number (#18-0023)

PARTICIPANT I.D. _____

9. Direct Oral Challenge

Low Dose (25 mg)

- a. Physical assessment and Vital Signs time =0 _____
- b. Oral Challenge administered _____
- c. Physical assessment and Vital Signs time =30 min. _____
- d. Results Explained to Subject _____

Full Dose (250 mg)

- a. Physical assessment and Vital Signs time =0 _____
- b. Oral Challenge administered _____
- c. Physical assessment and Vital Signs time =30 min. _____
- d. Results Explained to Subject _____

10. Participant Accessibility Survey _____

11. Notification Letter Provided _____

12. Is Action Plan Required?

Yes

No

Comments: _____

Completed By: _____ **Date:** _____
(Name, Observer Signature)

Reviewed By: _____ **Date:** _____
(Name, Site Investigator Signature)

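### In the direct-challenge group the written rule for giving 250 mg rests on vital signs (including peak flow) alone; no text makes a skin or swelling reaction to 25 mg a reason to stop

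*Protocol*

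**What the plan says.** Protocol 6.3.2 describes two steps for the DOC group. After 25 mg the subject is observed for 30 minutes (±10), "after which vital signs including peak flow will be repeated". The condition for the full dose then begins "If vital signs are within reasonable limits after the 30-minute", and if it is met the 250 mg dose is given. The physical exam is named only after 250 mg. Section 6.1.2.2 has the same order: a brief exam before the challenge, then "Administration of oral challenge (first step) of 25 mg of amoxicillin, vital sign assessment and, if indicated, administration of oral challenge (second step"), and at the end "Post-oral challenge brief PE, vital sign assessment and peak flow measurement". It does not define when the second step is indicated.

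Section 6.3 sets out the focused exam done before the oral challenge. It covers eyes, pharynx, lungs and skin, and one of its lines reads "Skin: Documentation of no maculopapular rash, disseminated pruritis or urticaria". Section 7.1.3 describes one repeat exam, at 60 minutes. Appendix A lists vital signs and the focused exam before and after the challenge.

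Appendix E, an observer checklist, goes further. Under item 9, after the 25 mg dose, it lists "Physical assessment and Vital Signs time =30 min", and it lists another assessment at time 0 before 250 mg. It attaches no pass or stop criterion to either.

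**The concern.** The 25 mg step is a test dose, and its purpose is to show a reaction before ten times as much drug is given (250/25 = 10). A rule that reads only vital signs and peak flow will catch hypotension, tachycardia and a fall in airflow. It will not by itself catch a reaction confined to skin or soft tissue. In Appendix C, one Moderate (Grade 2) cutaneous entry is "Generalized urticaria and/or periorbital edema or angioedema (not laryngeal, tongue or uvular"), with no vital-sign component. The subject's safety at the step-up is what is at stake.

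The setting adds weight. Section 2.2.6 notes that staff skills vary in these clinics and that many do not have a physician present all the time, so an explicit rule is worth more here than in an allergy clinic.

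**Working it through.** The main check is a reading of the text. The plan gives no figure of its own to reproduce.

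**Step 1. What each place requires between the doses**

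| Place | Check between 25 mg and 250 mg | Stated reason to withhold 250 mg |
|---|---|---|
| 6.3.2, dose steps | Vital signs including peak flow | Abnormal vital signs, by implication |
| 6.3.2, symptom paragraph | Placed after the full-dose step and tied to the final evaluation | None; record and treat |
| 6.1.2.2 | Vital signs | Second step conditional, condition undefined |
| 6.3 and 6.1.3 | Exam and exclusions before challenge | Not said to be re-applied before 250 mg |
| 6.3.3 | Normal vital signs and exam needed for a final negative | None between doses |
| 7.1.3, Appendix A | No exam placed between the doses | None |
| Appendix E, item 9 | Physical assessment and vital signs, after 25 mg and before 250 mg | None |

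**Step 2. Test case.** Take a subject with generalized urticaria 25 minutes after 25 mg and with normal pulse, respiration, blood pressure and peak flow. The condition in 6.3.2 is met, and the text directs 250 mg. No other place in the documents states a stop.

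**Step 3. Internal contrasts.** Urticaria, rash or angioedema at the exam in 6.3 would bar the 25 mg dose, yet nothing re-applies that bar before the larger dose. In the skin-test group the comparable step-up does have a stop: under 6.2, intradermal testing is not done after a positive or uninterpretable prick test. SAP 7.5 plans to summarise the focused exam for the full dose only.

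**Step 4. Rough size.** Inputs are from Protocol 2.2.3, 4.1 and 8.2.

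- Subjects: 5 sites × 100 = 500; less the assumed 5% higher-risk, 500 × 0.95 = 475. With four sites, 400 × 0.95 = 380. Both are before the 6.1.3 exclusions and refusals.
- Four direct-challenge series with countable events: 4 of 156 allergy mediated; 2 of 806 acute; 3 of 83 immediate (3.6%); 5 of 328 cutaneous (1.5%). Sum 14/1373 = 1.02% (exact 95% CI 0.56% to 1.70%); × 475 = 4.8. Endpoints differ between series. The randomised comparison with no events is left out because its arm size is not given.
- The inpatient series of 942 patients used the prescribed B-lactam as its test dose and had 14 reactions within an hour. Adding it gives 28/2315 = 1.2%; × 475 = 5.7.
- Reactions described as skin events number 3 + 5 = 8. Over all four series, 8/1373 = 0.58%; × 475 = 2.8. This treats six events of undescribed type as non-skin. Over only the two series that describe skin events, 8/411 = 1.9%; × 475 = 9.2.
- Share starting after 25 mg: not in the documents. At an assumed 10% to 50%, the skin counts become 0.3 to 1.4 (from 2.8) and 0.9 to 4.6 (from 9.2). For 380 subjects they are 0.2 to 1.1 and 0.7 to 3.7.

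None of these is an upper limit. The assumed share drives every count, and the undescribed events could be skin reactions. Working the other way, some skin reactions also move vital signs, and staff may stop on visible hives.

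**The case against.** The strongest reply is that the protocol, read as a whole, already covers this. Appendix E lists an assessment on both sides of the step-up and treats each dose as its own challenge. The exclusions in 6.3 and 6.1.3 can then be read as applying again before 250 mg. Section 6.1.2.2 makes the second step conditional, 7.1.3 calls for assessment of urticaria, rash and angioedema after challenge, and 6.3.3 treats a reaction as an outcome. Giving 250 mg to someone just treated for hives would mean ignoring all of this. The Oral Challenge Qualification Checklist (6.3) and the Manual of Procedures (6.6.4) are also not among the documents and may hold a stop rule.

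Much of that stands. The exam is intended, and staff may well stop. But the re-application of the exclusions is a plausible reading that is nowhere stated, while 6.3.2 does state when the dose is given. If the manual or checklist holds the stop, only alignment of the wording is needed.

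A reader might infer three stronger things that the documents do not support:

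- *That no exam takes place between doses.* Appendix E lists one.
- *That a circulatory or airway reaction passes the gate.* Vital signs and peak flow are in it.
- *That prevalence or negative predictive value is biased.* Section 6.3.3 says "Final outcomes of the oral challenge will be recorded on a CRF as no reaction (negative), reaction (positive) or unevaluable" and does not distinguish the dose, so a reaction to 25 mg falls under the same outcome.

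**Conclusion.** The point holds as a gap in the written dose-release rule. What is missing is a stop criterion, together with agreement between 6.3.2, 6.1.2.2 and Appendix E. It is a safety matter only. The sample size and the interval methods are unaffected, and the documents do not show that any site would in practice dose through a visible reaction.

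Few subjects would be affected, but the number cannot be bounded from the documents, because the share of reactions that start after 25 mg is not given. The illustrative counts rest on that assumed share and on pooling series with different endpoints. The reading of the text rests on neither. This is a cheap improvement.

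**What to change.** Amend 6.3.2 along these lines:

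> Thirty minutes (±10) after 25 mg, vital signs (including peak flow) and the focused PE are repeated, as in Appendix E. The 250 mg dose is given only if both are within reasonable limits and none of the focused-PE exclusions in 6.3 (angioedema, stridor, wheezing, rash, disseminated pruritis, urticaria) is present. Otherwise the challenge stops, and the event is treated, graded and recorded under 6.3.3. Symptoms reported without signs prompt clinician review before the second dose.

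In 6.1.2.2, define when the second step is indicated by reference to this rule. Align 7.1.3 and Appendix A with Appendix E. Leave the definition of a positive result in 6.3.3 as it is; a new rule on which complaints count as positive would change a primary outcome and does not belong in a safety amendment.

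The cost is mainly wording. Sites that already follow Appendix E add no exam. If none did, an assumed 3 to 5 minutes each gives 475 × 3/60 = 24 to 475 × 5/60 = 40 staff hours in all, or about 5 to 8 per site over five sites. Clinician review would be rare. Subjective complaints ran at 2.9% in the 806-patient series, so 0.029 × 475 = 13.8, and at the same assumed 10% to 50% about 1 to 7 subjects would need it before the second dose.
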